#### **Current Practice**

The Food and Drug Administration has approved both drugs proposed in this study (fluoxetine and bupropion) as standard therapy for MDD. The unfortunate reality is that most ESRD/HD patients that develop MDD are never treated. When antidepressants are prescribed for MDD in any patient with another co-occurring condition, they are selected based on the individual prior treatment history and contraindications for the patient. While neither of the medications being studied is contraindicated in ESRD/HD patients, dose adjustments are made due to differences in excretion rates.

# 3. Study Design

The current study proposes to randomly assign 40 CKD patients with MDD to 12 weeks of open label, flexible dose treatment with either bupropion (N=20) or fluoxetine (N=20).

[NOTE: We are requesting to enroll up to 50 subjects/with 40 completers. One of the outcome measures will be the number of weeks of treatment that a person completes. This is a preliminary feasibility and pilot study, so establishing an estimate of drop out rate will be important for when we design the "definitive" study in the future.]

# **4. Study population** is defined as CKD patients with chronic kidney disease with MDD. **Inclusion Criteria**

- age 30-70 vrs:
- meet the Diagnostic and Statistical Manual of Mental Disorders, 4th Edition (DSM-IV) criteria for MDD;
- have a Ham-D score > 17
- if receiving any of these medications, on a stable or maintenance dose of iron or erythropoietinstimulating agents, statins, angiotension receptor blockers and/or angiotension converting enzyme inhibitors, phosphate binders and vitamin D receptor analogs as these agents may influence cytokines proposed in the study;
- serum albumin of ≥ 3.2 g/dl, serum phosphate of <6.5 mg/dl, and serum hemoglobin of ≥9 mg/dl in two consecutive blood tests [subjects failing screening due to these blood tests will be allowed to be re-screened in 30 days];

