#### Choices of bupropion and fluoxetine for the treatment:

Bupropion is unique amongst antidepressants because it selectively blocks reuptake of NE and DA without having appreciable affinity for postsynaptic receptors including histamine, α- or β-adrenergic, 5-HT, or acetylcholine [30, 88]. This confers a favorable side effect and safety profile [89], absence of weight gain [90] or somnolence [91]; side effects frequently reported by HD patients with other antidepressants [92-95]. Bupropion has no clinically significant effects on the cardiovascular system (e.g., heart rate, blood pressure, QTc interval) in patients with MDD [96]. It can increase the incidence of seizures [97] in a dose-dependent (>450 mg/day) [30] fashion in patients with a history of seizures; therefore it is contraindicated in these patients. Bupropion may preferentially reduce a subset of symptoms of MDD common in medically ill patients, including fatigue, drowsiness, cognitive dysfunction, anhedonia, and mental concentration [98, 99]. In healthy humans, after oral administration, bupropion is rapidly and ~100% absorbed by the intestine, metabolized in the liver, and excreted via kidney. The hepatic cytochrome P450 (CYP) 2B6 catalyzes bupropion to a primary active metabolite, hydroxylbupropion. Several studies [62, 100, 101] have provided guidelines and recommendations about antidepressant agents in patients with ESRD/HD. One study [80] determined the PK of bupropion and its active metabolites in HD patients following a single 150-mg oral dose and found comparable PK profile to individuals with normal renal function. Compared with controls, hydroxyl-bupropion demonstrated a >2fold greater AUC and substantially increased t1/2, indicating reduced clearance. Based on these data, the authors [80] suggested an oral dose of 150 mg bupropion every 3 days in HD patients.

While it has been suggested that antidepressants may in general reduce inflammation, research data suggests that SSRIs and tricyclic antidepressants may not. Other hand, there has been considerable recent interest in the anti-inflammatory effects of bupropion, although more research is needed [102]. Brustolim et al. [33] demonstrated that bupropion significantly reduced the levels of TNF- $\alpha$  in mice challenged with lipopolysaccharide and suggested that this effect might have important clinical consequences. In case reports, Kast and Altschuler [35, 36] proposed the potential anti-inflammatory

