#### **Exclusion Criteria**

- meet DSM-IV criteria for Bipolar Disorder or other psychotic disorder in the month prior to screening:
- are taking antidepressants, anti-anxiety medications, or hypnotics (including Zyban for smoking cessation);

Version #: 17, IRB #203076

PI: [name]

- failure to respond to or tolerate bupropion or fluoxetine in the past
- allergic to fluoxetine or bupropion
- known history of HIV/AIDS; No testing will be conducted for screening purposes
- known history of alcohol or drug abuse or dependence within the month prior to screening based on clinical records;
- history of myocardial infarction or heart failure within one month of screening or a history of seizures or stroke at any point;
- history of chronic liver disease and diagnosis of hepatic encephalopathy based on clinical records;
- · currently diagnosed with cancer or receiving any cancer treatment;
- history of any infection within the last 2 weeks;
- currently taking any antibiotics, anti-inflammatory (low dose aspirin is acceptable), and immune-modulator agents;
- recorded noncompliance with dialysis schedules; and
- currently participating in clinical or behavioral intervention studies.

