After consent, subjects will be interviewed by a study staff for eligibility, including a review of medical records (if available), clinical interview, physical examination, routine blood tests, and EKG, if not already available (within one month). Psychiatric diagnosis will be established after interview using the Mini International Neuropsychiatric Interview (MINI) [75], depressive symptoms will be assessed with the Hamilton Depression (HAM-D) Scale [76], and cognitive status will be assessed using the n-back and MSIT tasks [77] and the Modified Mini Mental Status (3MS) Examination [78]. Pain will be characterized with the Physical and Psychological Pain Scale [142]. Pressure pain threshold will be measured with an Algometer [143]. Thermal pain sensitivity will be characterized with Quantitative Sensory Testing (QST). Delay discounting, MSIT and n-back will be the primary measures of cognitive function and the 3MS will be used for comparison to other studies. History of prior antidepressant treatment and response will be obtained using the Antidepressant Treatment Response Questionnaire (ATRQ) [79]. Given the underrecognized role of dental and gum disease in systemic inflammation a basic noninvasive dental evaluation will be performed by [name] at UAMS Dental Hygiene Clinic. Dialysis dose, pre- and post-dialysis body weight and blood pressure, serum urea nitrogen, albumin, serum phosphate hemoglobin, calcium, parathyroid hormone, vitamin D and lipid profile will be extracted. Measures of dialysis adequacy (kt/V) will also be extracted.

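### The hemoglobin entry limit is printed in mg/dl, so as written no patient can fail it; the unit needs correcting

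*Combined protocol and SAP*

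**What the plan says.** The Inclusion Criteria in section 4 put three laboratory limits in one bullet. The first two are "serum albumin of ≥ 3.2 g/dl, serum phosphate of <6.5 mg/dl". The third is "serum hemoglobin of ≥9 mg/dl in two consecutive blood tests". The bullet then adds that "subjects failing screening due to these blood tests will be allowed to be re-screened in 30 days".

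Hemoglobin appears again in section 6, Research Plan, among values taken from the record: "serum urea nitrogen, albumin, serum phosphate hemoglobin, calcium, parathyroid hormone, vitamin D and lipid profile will be extracted". No unit or limit is given there.

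A separate wording question arises in the Exclusion Criteria, where one bullet reads "history of chronic liver disease and diagnosis of hepatic encephalopathy based on clinical records". Nothing elsewhere says whether both conditions must be present or either is enough.

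**The concern.** An eligibility limit is applied to every candidate, so its unit is part of the decision rule. A hemoglobin floor of 9 mg/dl lies far below any value a candidate could have, so it cannot do the work that the bullet assigns to it.

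Two things are at stake, both modest.

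- **Screening and the text can disagree.** If staff apply 9 g/dl, a patient at 7 g/dl is turned away although the written criterion was met. If they apply the text, that patient is admitted. The General Methods section plans to tabulate screen failures by reason, as feasibility data for a later trial. On the printed text, a failure for hemoglobin cannot arise.
- **Fatigue is a Hypothesis 2 outcome.** That low hemoglobin contributes to fatigue is general medical knowledge, not something the documents state. With 20 patients planned per arm, each patient is 1/20 = 5% of an arm.

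The liver bullet raises a smaller issue. Two screeners could classify the same patient differently. The Background (Choices of bupropion and fluoxetine for the treatment) describes bupropion as "metabolized in the liver, and excreted via kidney", so liver status bears on drug exposure.

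**Working it through.** **Hemoglobin: inputs.** The printed limit is 9 mg/dl, the albumin limit in the same bullet is in g/dl, and the phosphate limit is in mg/dl (all section 4, Inclusion Criteria). The conversion is 1 g = 1000 mg. I take hemoglobin to mean the ordinary blood concentration. The documents give no distribution of it, so I assume values from 3 to 18 g/dl to show the range. The plan has no derived figure to reproduce here.

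**Step 1: convert the limit.** 9 mg/dl ÷ 1000 = 0.009 g/dl. Relative to 9 g/dl, the factor is 9 ÷ 0.009 = 1000.

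**Step 2: apply both versions to the assumed values.**

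| Assumed hemoglobin (g/dl) | Same value (mg/dl) | Meets ≥9 mg/dl | Meets ≥9 g/dl |
|---|---|---|---|
| 3 | 3000 | yes | no |
| 5 | 5000 | yes | no |
| 7 | 7000 | yes | no |
| 9 | 9000 | yes | yes |
| 12 | 12000 | yes | yes |
| 18 | 18000 | yes | yes |

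Every value passes the printed limit. Under g/dl, the values 3, 5 and 7 fail.

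**Step 3: look for a correction elsewhere.** The only other place that lists hemoglobin as a measurement is the Research Plan, which gives neither unit nor limit. The bullet itself uses g/dl for albumin and mg/dl for phosphate, so both units were in use when it was written, and a slip from one to the other is easy to make.

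**Liver bullet: the two readings.**

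| Chronic liver disease | Hepatic encephalopathy | Excluded if both needed | Excluded if either is enough |
|---|---|---|---|
| no | no | no | no |
| no | yes | no | yes |
| yes | no | no | yes |
| yes | yes | yes | yes |

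The readings agree when neither or both conditions are present. They differ when only one is present; the case of interest is chronic liver disease without recorded encephalopathy. The rest of the list does not settle the matter. One bullet joins separate grounds with *or*: "history of myocardial infarction or heart failure within one month of screening or a history of seizures or stroke at any point". Another joins separate grounds with *and*: "currently taking any antibiotics, anti-inflammatory (low dose aspirin is acceptable), and immune-modulator agents". Nobody would take the second to require all three drug classes at once.

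**The case against.** The best defence is practical. A laboratory report in g/dl would be read against the number 9, and the bullet plainly intends a working limit because it tests twice and provides for failures. On this view nobody is wrongly admitted, and the error is editorial. I accept that this is the likely course of events. It does not remove the defect: the approved text is the criterion against which eligibility and deviations are judged, and it states a limit that cannot operate.

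Four stronger readings may tempt a reader, and the documents do not support them.

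- *The re-screening provision is empty.* It is not. It covers all three tests, and the albumin and phosphate limits work as printed. Only its hemoglobin part has no effect.
- *Anemia treatment will distort the fatigue comparison.* Nothing shows that severely anemic patients have been or will be enrolled. The bullet before this one already asks for steady dosing of iron and erythropoiesis-stimulating agents in patients who take them.
- *The liver exclusion requires both conditions and so fails to screen.* The bullet on antibiotics and related drugs shows that *and* can join separate grounds in this list. Even the joint reading still excludes patients who have both conditions, and nothing shows that a narrower exclusion would be unintended.
- *Patients with chronic liver infection would distort the cytokine analyses.* The section on the choice of drugs presents the hepatitis B material as case reports proposing a possible effect. Recent infection and current immune-modulating drugs are separate exclusions that may already catch some such patients. Drug and metabolite levels are also measured at weeks 4 and 12.

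**Conclusion.** The hemoglobin limit is wrong as written. It is an operative inclusion threshold, a factor of 1000 below the same number in g/dl, and nothing elsewhere in the protocol or SAP corrects it. Read literally, it screens out nobody.

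The conclusion that g/dl was meant rests on physiology and on the albumin unit beside it; the documents never say so. The effect on who enters the trial is probably small and cannot be estimated, because the documents give neither hemoglobin values for the screened population nor an account of how the limit is applied.

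The liver wording is an ambiguity, not an error. It merits a clarification and no more, and this review takes no position on which meaning is right.

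**What to change.** 1. Correct the unit of the hemoglobin limit in section 4, Inclusion Criteria. The context points to g/dl, and the sponsor should confirm it.
2. Compare the records of patients already screened with the corrected limit. List any who were enrolled but would not have met it, and any who were turned away on hemoglobin although they met the printed text.
3. In the same amendment, state whether the liver bullet in the Exclusion Criteria applies when both conditions are present or when either one is. The choice is the sponsor's.

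The cost is a one-word correction, one clarifying phrase and a pass through the screening records. If the corrected limit differs from what staff have been applying, the number of screen failures may change slightly.

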# For patients not on HD or Peritoneal Dialysis

• Estimated glomerular filtration rate below 59 mL/min per 1.73 m^2.

#### For patients on HD

- have patent and non-infected arteriovenous fistula or graft;
- are receiving maintenance HD 2-3 times per week;

# For patients on Peritoneal Dialysis

• compliance with outpatient visits for the past two months;

#### **Exclusion Criteria**

- meet DSM-IV criteria for Bipolar Disorder or other psychotic disorder in the month prior to screening:
- are taking antidepressants, anti-anxiety medications, or hypnotics (including Zyban for smoking cessation);

Version #: 17, IRB #203076

PI: [name]

- failure to respond to or tolerate bupropion or fluoxetine in the past
- allergic to fluoxetine or bupropion
- known history of HIV/AIDS; No testing will be conducted for screening purposes
- known history of alcohol or drug abuse or dependence within the month prior to screening based on clinical records;
- history of myocardial infarction or heart failure within one month of screening or a history of seizures or stroke at any point;
- history of chronic liver disease and diagnosis of hepatic encephalopathy based on clinical records;
- · currently diagnosed with cancer or receiving any cancer treatment;
- history of any infection within the last 2 weeks;
- currently taking any antibiotics, anti-inflammatory (low dose aspirin is acceptable), and immune-modulator agents;
- recorded noncompliance with dialysis schedules; and
- currently participating in clinical or behavioral intervention studies.

# Recruitment Process—Identifying Potential Subjects

Subjects will be recruited from the UAMS Kidney Center, other outpatient UAMS clinics, UAMS Hemodialysis Center and other local dialysis centers using flyers, electronic dissemination of the flyer to UAMS physicians and/or newspaper ads. Referring physicians will be invited to provide the information to patients who they feel are appropriate for the study and, if the patient expresses an interest in participation or obtaining more information, the physician will provide the contact information of the study staff to the patient, who will voluntarily choose whether to contact the study staff for screening. Release of information/consent documents will be obtained prior to accessing patient clinical information. Prior to beginning the protocol and after obtaining patient's consent, study physicians will discuss the merits of a patient's participation in the study with the patient's hemodialysis physician.

Patients seeking information about the study will initiate phone contact with study staff for initial screening regarding inclusion and exclusion criteria. A partial HIPAA waiver will be requested from the IRB for phone screening purposes only. Subsequent access to clinical information will require written release of information/consent by the patient.

Each potential subject will contact the study staff by phone for initial screening regarding inclusion and exclusion criteria. Patients, who appear to meet inclusion and exclusion criteria and indicate agreement for the study team to contact their treating physician, will be scheduled to come in for a face-to-face meeting, be provided with study information, sign informed consent/HIPAA Authorization and undergo initial evaluation. After consent/authorization is signed by the subject, the research staff will contact the treating physician to discuss the subject's participation, provide medical records release, and obtain medical information from the treating physician.

# 5. Consent Process

Patients, who contact the research staff, appear to meet inclusion and exclusion criteria and indicate during this contact that they will agree to allow the study team to contact their treating physician, will be scheduled for a face-to-face meeting for informed consent and initial evaluation either at the UAMS Psychiatric Research Institute (PRI; 4th floor) or their dialysis site. Consent will be obtained prior to any research procedures taking place. The potential subject will be encouraged to bring a family member with them for this appointment. During this meeting, a member of the research staff will describe the study and review the IRB-approved consent form using lay terms with special emphasis on the risks and benefits, in an objective way. The team member will make attempts to answer & clarify or address any questions or concerns the subject (and family member) may have during this process. Ample time will be given to the subject to make a voluntary decision. The study information, inclusion and exclusion criteria, and consent documents will be reviewed. The study team member conducting the consent process will sign and date the consent form. The subject will be given a business card of the study team so that he/she can discuss any further questions or concerns that may arise in the future. A copy of the signed and dated consent form will be given to the subject for his/her record.

Version #: 17, IRB #203076

PI: [name]

Subjects will be encouraged to take the consent form at home to read, understand, and discuss with his/her family members and or primary care physician. In this situation, subject will be contacted after one week to learn his/her decision to participate in the study and a subsequent meeting scheduled to sign the documents. An interested subject must sign the consent form in presence of the study personnel. Patients will be scheduled for consent/initial evaluation appointments during the initial phone screening. This appointment will take place between 1-14 days, giving subjects ample time to make a voluntary decision. There is no specific waiting time limit.

Participation of an eligible subject in this clinical trial is a voluntary process. Subjects will not be coerced or influenced by the study personnel. In order to participate, subjects will have to voluntarily initiate a phone screening and subsequently come to a face-to-face consent/initial evaluation meeting. A research staff member or study investigator will conduct the consent process in order to minimize the possibility of undue influence from the treating physician on their hemodialysis team. Subjects will be informed that participation is voluntary and not participating will not affect the delivery of the routine health care. They and their treating physicians will be informed that the medications being used in the current study are routinely available and relatively inexpensive to obtain. They do not have to participate in this study to receive any of the treatment options.

Subjects are randomly assigned to open label treatment with one of two medications. Therefore, there are two groups:

- Bupropion group:
  - For patient not on hemodialysis, oral administration of bupropion SR tablet at a dose of 150 mg daily. Bupropion SR doses will be adjusted upward or downward based on tolerability and response.
  - For patient on hemodialysis or peritoneal dialysis, oral administration of bupropion SR tablet at a dose of 150 mg on the 1st and the 3rd dialysis day of each week. Bupropion SR doses will be adjusted upward or downward based on tolerability and response.
- Fluoxetine group: Oral administration of fluoxetine tablet will be started at a dose of 10 mg/day for the first week and then increased, as tolerated to 20 mg/day for weeks 2–4. After this, doses will be adjusted based on clinical response and side effects up to a maximum dose of 60 mg/daily by week 10.

Although non-English speaking participants are not anticipated, there is an unlikely possibility that we may recruit a Spanish-speaking individual. If this occurs we will submit the translated materials and certification of translation to the IRB for approval prior to enrolling the subject. The principal investigator is fluent in Spanish (reading, writing, speaking) and will obtain consent from any Spanish speaking subjects. Study staff will assess each subject's understanding of the study procedures, including risks and benefits, during the initial evaluation process. A Spanish-speaking physician will interview Spanish-speaking subjects during the initial evaluation to determine their understanding of the materials, and subjects will be given the option of having study materials in their preferred language. Since the possibility of recruitment of a non-English speaking participant is unlikely in this small population, we will not submit translated materials for approval unless necessary.

## 6. Research Plan

The current study proposes to recruit up to 50 participants in order to have 40 completers. Eligible CKD patients with MDD will be randomly assigned to 12 weeks of open label, flexible dose treatment with either Bupropion SR (N=20) or Fluoxetine (N=20). Patients will be recruited from the UAMS dialysis center or other local dialysis centers via flyers, referral by their treating physician and/or newspaper ads. Written consent will be obtained before any study procedures. Subjects are randomly assigned to open label treatment with one of the following:

• Bupropion group:

Version #: 17, IRB #203076

PI: [name]

 For patient not on hemodialysis or peritoneal, oral administration of bupropion SR tablet at a dose of 150 mg daily. Bupropion SR doses will be adjusted upward or downward based on tolerability and response.

- For patient on hemodialysis or peritoneal dialysis, oral administration of bupropion SR tablet at a dose of 150 mg on the 1st and the 3rd dialysis day of each week. Bupropion SR doses will be adjusted upward or downward based on tolerability and response.
- Fluoxetine group: Oral administration of fluoxetine tablet will be started at a dose of 10 mg/day for the
  first week and then increased, as tolerated to 20 mg/day for weeks 2–4. After this, doses will be
  adjusted based on clinical response and side effects up to a maximum dose of 60 mg/daily by week
  10.

After consent, subjects will be interviewed by a study staff for eligibility, including a review of medical records (if available), clinical interview, physical examination, routine blood tests, and EKG, if not already available (within one month). Psychiatric diagnosis will be established after interview using the Mini International Neuropsychiatric Interview (MINI) [75], depressive symptoms will be assessed with the Hamilton Depression (HAM-D) Scale [76], and cognitive status will be assessed using the n-back and MSIT tasks [77] and the Modified Mini Mental Status (3MS) Examination [78]. Pain will be characterized with the Physical and Psychological Pain Scale [142]. Pressure pain threshold will be measured with an Algometer [143]. Thermal pain sensitivity will be characterized with Quantitative Sensory Testing (QST). Delay discounting, MSIT and n-back will be the primary measures of cognitive function and the 3MS will be used for comparison to other studies. History of prior antidepressant treatment and response will be obtained using the Antidepressant Treatment Response Questionnaire (ATRQ) [79]. Given the underrecognized role of dental and gum disease in systemic inflammation a basic noninvasive dental evaluation will be performed by [name] at UAMS Dental Hygiene Clinic. Dialysis dose, pre- and post-dialysis body weight and blood pressure, serum urea nitrogen, albumin, serum phosphate hemoglobin, calcium, parathyroid hormone, vitamin D and lipid profile will be extracted. Measures of dialysis adequacy (kt/V) will also be extracted.

Participants will receive the study medication during the baseline assessment and instructed to begin the medication on day 1 (1st dialysis day) of week 1 of the study. For patient on hemodialysis or peritoneal dialysis, generic bupropion SR will be dosed at 150 mg on the 1st and the 3rd dialysis day of each week with doses adjusted upward or downward based on tolerability. The initial dose of bupropion-SR is based on the findings of Worrall et al [80], who measured plasma bupropion levels in a pharmacokinetic study of bupropion in HD patients. For patient not on hemodialysis or peritoneal dialysis, generic bupropion SR tablet will be dosed at 150 mg daily. Bupropion SR doses will be adjusted upward or downward based on tolerability and response. Fluoxetine will be started at 10 mg/day for the first week and then increased, as tolerated to 20 mg/day for weeks 2–4. After this, doses will be adjusted based on clinical response and side effects up to a maximum dose of 60 mg/daily by week 10 [62]. At the week 12 visit, the participants will stop the medication or may undergo a 1-2 week taper (depending on maintenance dose) if they are on a dose of fluoxetine that is higher than 20 mg.

Subjects will be seen during weeks 1, 2, 3, 4, 6, 8, 10, and 12 in face-to-face meetings by a rater blind to study medication and a study physician for Ham-D ratings, CGI, medication accountability, and measurement of adverse events. On weeks 5, 7, 9 and 11, subjects will come in to return the previous week's pill bottles and pick up the current week's medication. Table 1 shows study procedures. Medication will be prepared by UAMS Research Pharmacy, labeled with the directions for use and contact information, and given to participants by study staff on a weekly basis. Compliance will be monitored using the MAFV at each scheduled encounter and by analysis of antidepressant blood levels. Results of a second EKG done during week 4 will be reviewed to ensure QTc interval is less than 500 msec.

In order to control for the potential confound of chronic pain we will characterize it with the physical and psychological pain scale and with two objective measures, i.e. the pressure pain threshold and the Quantitative Sensory Test (QST).

Version #: 17, IRB #203076

PI: [name]

Given that dental disease (gum disease and caries) is the main source of increased inflammation in the general population we aim to control for this confound for our Specific Aim 3 by having a baseline and end of study dental assessment.

